It will be followed by an examination of the autonomic nervous system [ANS] functioning and the ANS - central nervous system [CNS] – enteric nervous system [ENS] electrophysiological coupling by using different electrophysiological tools (electrogastrogram [ECG], galvanic skin responses [GSR], photoplethysmography [PPG], breathing belt, electrogastrogram [EGG], electroencephalogram [EEG]). All the electrophysiological recordings will be synchronized and an acclimatization period will be respected. The recordings will be done seated in a quiet room. The physiological measures will ever be recorded at rest (30 minutes, eyes-closed), during a reactivity emotional task (reactivity period) and in the recovery period following the task (30 minutes, eyes-closed). Electrophysiological data will be collected by the acquisition systems BIOPAC® (MP 150, CEROM, France) and BioSemi®. The ECG data will be recorded using 3 single use and adhesive electrodes placed on the inner side of the right wrist, on the right shoulder and on the left side in accordance with the DII standard position (Einthoven). Physiological data recorded are related to the heart rate variability [HRV]. The breathing effects on the HRV will be controlled by means of the breathing rate recording using a breathing belt. The GSR data will be recorded using 2 skin sensors placed on the third phalanx of the forefinger and of the middle finger of the left hand. Physiological data recorded are related to the cholinergic sympathetic activity (tonic GSR / phasic GSR). The PPG data will be recorded using a finger sensor. Physiological data recorded are related to the adrenergic sympathetic tone and allowing a record of the blood pulse waves associated with the heart rate. The EGG data will be recorded using 6 single use and adhesive electrodes placed on the skin of the abdomen. Physiological data recorded are related to the gastric electrical activity. The EEG data will be recorded using a EEG headsets including 64 electrodes. The EEG is related to the brain activity generated by the neural functioning. The emotional reactivity task will be explained carefully.

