Concerning the online questionnaires: the package 1 is constituted by the SSQ6, the MAIA-2 and the STAI Y-B. The package 2 is constituted by the Brief-Cope, the BFI-N and the CTQ. The package 3 is constituted by the DHS. The package 4 is constituted by the BVAQ-B and the LE

II : Statistical analysis plan

Independent variables

Analysis A:

The participants will be separated into two inter-subject groups:

- An experimental group performing BFB technique in the intervention phase (T2-T3)
- A control group no performing an exercise in the intervention phase (T2-T3)

The participants won't be informed of the condition to which they belong.

Independent variables

- Measurement time (T1 / T2 / T3) intra-subject
- Group (experimental group / control group) inter-subject

Analysis B:

The participants will be separated into two inter-subject groups performing by a cluster analysis (HF or RMSSD) in the first session (T1):

- A dysfunctional neurovegetative profile (low vagal tone + low vagal flexibility) group
- A functional neurovegetative profile (high vagal tone + high vagal flexibility) group

The participants won't be informed about their neurovegetative profile. We will include all the participants.

Independent variable

- Neurovegetative profile (dysfunctional profile / functional profile) inter-subject

Analysis C:

The participants will be separated into two inter-subject groups performing by a cluster analysis (HF or RMSSD) in the first session (T1):

- A dysfunctional neurovegetative profile (low vagal tone + low vagal flexibility) group
- A functional neurovegetative profile (high vagal tone + high vagal flexibility) group

The participants won't be informed about their neurovegetative profile. We will include only the experimental group performing the BFB technique.

Independent variables

- Neurovegetative profile (dysfunctional profile / functional profile) inter-subject
- Measurement time (T2 / T3) intra-subject

Dependent variables

Physiological variables:

ECG –HRV:

- HF (0.15-0.40 Hz – high frequency) frequency-domain parameter
- LF (0.04-0.15 Hz – low frequency) frequency-domain parameter
- LF-0.1 Hertz (0.075-0.108Hz - spectral power of the low-frequency 0.1Hz band) frequency-domain parameter
- LF/HF (ratio of LF to HF power) frequency-domain parameter
- Total power (total power of the 0-0.40 Hertz band) frequency-domain parameter
- RMSSD (root mean square of successive RR interval differences) temporal-domain parameter

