- SDNN (standard deviation of all NN intervals) temporal-domain parameter
- EDR (ECG-derived-respiration)

GSR (tonic GSR / phasic GSR):

- SCR frequency: number of the spontaneous galvanic skin responses by periods
- SCR amplitude: amplitude of the spontaneous galvanic skin responses by periods
- Integrated skin conductance responses [ISCR]: area of the galvanic skin responses identified on the signal

PPG:

- Pulsatility index variation (PI): Transit time flow

Breathing belt:

- Breathing rate by cycles per minute

EGG:

- Dominant power
- Total power [0-0.15 Hertz]
- Slow-waves frequency per minute

EEG:

- Spontaneous brain rhythms: spectral power of the 0-30 Hertz band

Physiological adaptation to the aversive situation (emotional reactivity task):

HRV, GSR and PPG differences will be calculated to measure the physiological changes causing by the task compared to the resting and the recovery periods. The differences will be calculated as follows:

- Physiological reactivity during the task compared to the resting period (Δ = reactivity HRV – resting HRV / Δ = reactivity GSR – resting GSR / Δ = reactivity PPG – resting PPG)
- Physiological recovery following the task (Δ = recovery HRV – reactivity HRV / Δ = recovery GSR – reactivity GSR / Δ = recovery PPG – reactivity PPG)

- Physiological recovery following the task compared to the resting period (Δ = recovery HRV – resting HRV / Δ = recovery GSR – resting GSR / Δ = recovery PPG – resting PPG)

Psychological variables:

- Alexithymia score (BVAQ-B)
- Neuroticism score (BFI-N)
- Trait anxiety score (STAI Y-B)
- Style of coping (Brief Cope)
- Positive affectivity score (PANAS)
- State anxiety score (STAI Y-A)
- Depressive symptoms score (CES-D)
- Perceived-stress level (PSS)
- Coping flexibility + metacoping scores (CFS + VAS)
- Acceptance score (ICQ-18)
- Social support score (SSQ6)
- Interceptive sensitivity score (MAIA-2)
- Life satisfaction score (SWLS)
- Negative impact scores (LES)
- Frequency, severity and intensity scores (DHS)
- Abuse scores (CTQ)

Statistical analyses

All statistical analyses will be performed using IBM SPSS Statistics®, R software® and JASP®. The alpha value for statistical significance will set at $p<0.05$.

Analyses of the scores collected will be done in several stages:

- Highlighting outlier participants to exclude from our statistical analysis.
- All the conditions for application of statistical tests will be verified.

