- In the case of a failure to respect the conditions for parametric test application, we would make a data transformation to jointly improve normality and homogeneity residues. If the normality is failed and the homogeneity is respected, we would execute non-parametric tests.
- Analysis will be done on the subjects included. Analysis concerning the reactivity period (during the task) will be performed on the all blocs excepted the bloc 1².
- Main and secondary judgment criterions analysis will be performed by parametric tests or by non-parametric tests depending on the conditions for application:

• *Analyse A:*

- An ANOVA to repeated measurement with an intra factor (measurement time: T1 / T2 / T3) and an inter factor (group: experimental / control) on the physiological and psychological data collected.
- Student's test for independent samples will be performed on the psychological scores collected in the second session (T2) to account for the initial level of psychological states between the 2 groups.

² The bloc 1 will not be included in the final statistical analysis because is considered as a training bloc. This choice in accordance to the potential biases related to the increase of the sympathetic activity at the beginning of the task caused by a simple moving to action following the resting period.

- Contrasts will then be made by group on the scores in order to specify the effect of the condition on the physiological and psychological data.
- *Analyse B:*
 - K means non-hierarchical clustering will be performed with K = 2. To categorise participants depending on their resting neurovegetative profile (low vagal tone / high vagal tone) and on their dynamical neurovegetative profile (low vagal flexibility / high vagal flexibility), two K means non-hierarchical clustering will be performed with K = 2. One with HF or RMSSD and one with Δ HF or Δ RMSSD.
 - Student's test for independent samples (dysfunctional neurovegetative profile / functional neurovegetative profile) will be performed on the psychological vulnerability (trait scores) collected.
- *Analyse C:*
 - An ANOVA to repeated measurement with an intra factor (measurement time: T2 / T3) and an inter factor (neurovegetative profile: dysfunctional profile / functional profile) on the physiological and psychological data collected only into the experimental group performing the BFB technique.
- *Correlational analysis:*

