 - Regressions or the Pearson correlations will be performed in order to measure the inter-signal correlation (ECG-EGG-EEG)
 - Regressions or the Pearson correlations will be performed in order to test our hypothesis about the HF/RMSSD related to the "low vagal tone" profile will be more correlated to Δ HF/RMSSD related to the "low vagal flexibility" profile than to Δ HF/RMSSD related to the "high vagal flexibility" profile. As the same as HF/RMSSD related to the "high vagal tone" profile will be more correlated to Δ HF/RMSSD related to the "high vagal flexibility" profile than to Δ HF/RMSSD related to the "low vagal flexibility" profile

Additional analyses

- We will control the age effect and the gender effect.
- Some additional statistical analyses will be exploratory: stability of the resting and the dynamical neurovegetative endophenotypes before the control period (T1) and at the end of the control period (T2).
- Correlation between the LF 0.1Hz and the clinical outcomes.
- To confirm the physiological effects of the BFB (BFB vs pseudo-BFB) on the flexibility of the electrophysiological coupling concerning the brain-visceral axis.

Sample

Power analysis (G * Power; Faul et al., 2007) was performed to determine a priori the sample size needed for this study. The power analysis, for an ANOVA (repeated measures, within-between factors), was performed for an effect size (η_p^2) of .12 with a power of .95 on the main judgment criterion (HRV – vagal tone HF) and reported a necessary sample of at least 22 participants (Kudo et al., 2014; Paul & Garg, 2012; Wells et al., 2012). We decided to include at least 25 IBS patients SII (20 test & 5 control) and 22 PNES patients (20 test & 5 control) in accordance with the possible inclusion rate and the duration of the study.

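### Two of the three Deltas subtract the resting value that defines vagal tone, so a tone–flexibility correlation using either is biased downward, with no planned safeguard

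*Combined protocol and SAP*

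**What the plan says.** The SAP (Dependent variables, on physiological adaptation to the task) defines three HRV differences:

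- task minus rest: "Physiological reactivity during the task compared to the resting period (Δ = reactivity HRV – resting HRV"
- recovery minus task: "Physiological recovery following the task (Δ = recovery HRV – reactivity HRV"
- recovery minus rest: "Physiological recovery following the task compared to the resting period"

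The first and third contain resting HRV with a minus sign. The second does not contain it.

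Under Analyse B, patients are classed by two K-means clusterings of T1 data: "One with HF or RMSSD and one with Δ HF or Δ RMSSD". The first gives tone, from rest. The second gives flexibility, from a Delta that is not named. The two are combined into profiles such as "A dysfunctional neurovegetative profile (low vagal tone + low vagal flexibility) group".

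The correlational analysis then says: "Regressions or the Pearson correlations will be performed in order to test our hypothesis about the HF/RMSSD". The hypothesis is comparative. Tone in one tone profile should correlate more strongly with Delta in the matching flexibility profile than in the opposite one. No test is named for that comparison.

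On the recordings, Part I says: "The physiological measures will ever be recorded at rest (30 minutes, eyes-closed". The same rest recording is made at T1 and T2, and biofeedback training starts only at the end of T2.

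**The concern.** If flexibility is task minus rest or recovery minus rest, one measured quantity sits on both sides of the correlation. A patient whose T1 resting HF happens to read high is scored as having more tone and, for the same reason, a lower signed Delta. A negative correlation can then appear when true change is unrelated to true tone, and a real positive one can be hidden.

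Whether this helps or hurts the hypothesis depends on a choice the plan leaves open. If a larger fall is high flexibility, the artefact looks like a link between high tone and high flexibility. If a larger rise is high flexibility, it works against such a link.

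Nothing planned separates the shared error. Control for age and gender, the breathing record, and the outlier and assumption checks do not address it. The exploratory T1/T2 stability analysis is not a safeguard either, because a correlation coupled within each session would recur at both.

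**Working it through.** **The plan's own figure.** The only sample-size figure, 22, concerns the repeated-measures ANOVA. With f² = .12/.88 = .136, 2 groups, 3 times, and an assumed correlation of .5 and ε of 1, λ = 22 × 3 × .136/.5 = 18.0. Power is .964 at 22 and .944 at 20, so 22 reproduces. It has no bearing on this point, and the plan gives no figure for the correlation.

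**Inputs.** N = 50 (40 + 10, Part I), or 47 (25 + 22, as written under Sample). Alpha is .05. The documents give neither the reliability of resting HF/RMSSD nor the spread of true change, so both are assumed and varied.

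**Model.** Rest = T + e₁ and task = T + D + e₂. True tone T has SD 1. True change D has SD s and is independent of T. Error variance is v = (1 − R)/R, where R is reliability. Then

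corr(rest, task − rest) = −v / √[(1 + v)(s² + 2v)].

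The chance that a Pearson test at N = 50 rejects is approximately Φ(|atanh r| × √47 − 1.96).

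| R | s | v | r | Approximate rejection | Simulated |
|---|---|---|---|---|---|
| .7 | .3 | .429 | −.429/√(1.429 × .947) = −.37 | 76% | about 77% |
| .8 | .5 | .250 | −.250/√(1.25 × .75) = −.26 | 44% | about 44% |
| .9 | .8 | .111 | −.111/√(1.111 × .862) = −.11 | 12% | about 12% |

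At N = 47 the middle row gives about 42% to 43%. With recovery minus task, or with a resting value whose error is separate from the Delta's, r is 0 and rejection is about 5%.

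**Error shared by rest and task.** All periods are recorded in one session, so part of the error may be common to rest and task and cancel in the Delta. If a fraction c is common, r = −(1 − c)v / √[(1 + v)(s² + 2(1 − c)v)]. At R = .8 and s = .5:

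- c = ¼: r = −.1875/√(1.25 × .625) = −.21, rejection about 32%
- c = ½: r = −.125/√(1.25 × .5) = −.16, about 19%
- c = ¾: r = −.0625/√(1.25 × .375) = −.09, about 9% to 10%

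**A real association.** Let change be .2 × tone plus an independent part with SD .5, so true r = .2/√(.04 + .25) = +.37. At R = .8 the coupled correlation is (.2 − .25)/√(1.25 × .79) = −.05. With rest split into halves it is .2/√(1.5 × 1.04) = +.16.

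**Without an error model.** For task/rest SD ratio k and rest–task correlation ρ, corr = (kρ − 1)/√(1 + k² − 2kρ). At ρ = .8 this is −.32 for k = 1, nil for k = 1.25 and +.22 for k = 1.5. The observed sign therefore cannot be predicted from the documents.

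**The stated comparison between cells.** Within tone-by-Delta cells the artefact is small: −.05 to −.10 where tone and signed Delta are both low or both high, and −.06 to −.15 in the other two cells (reliability .7 to .9). Suppose cells are read one by one, at R = .8 and s = .5. The hypothesised pattern (matching cell significant, its counterpart not) then appears in about 15% of trials with the coupled Delta and 8% to 10% with a decoupled one. A Fisher z test of the difference rejects in about 5% either way. Its power is low: for r of .5 against 0, 19% with cells of 17 and 8, and 24% with 13 and 12.

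**Profile counts.** At R = .8 and s = .5, patients in the two matching profiles number 29 of 50 (fall = high) or 21 (rise = high) with the coupled Delta, against 25 in truth.

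**The case against.** The strongest reply is that the 12% to 77% belongs to one overall tone–Delta correlation, whereas the SAP's hypothesis compares correlations between cells. This stands. For that comparison the coupling adds only a few percentage points when cells are read singly, and essentially nothing under a formal test.

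Second, rest and task are recorded in one session, so independent errors is an unfavourable assumption. This also stands, and the range above is shown with and without it.

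Third, the sponsor may intend recovery minus task, which has no shared term. That is possible, and the point is conditional for this reason. The wording equally permits the two Deltas that do share rest.

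A reader might infer that the shifted profile counts invalidate Analyses B and C, or that the profiles should be rebuilt from split rest. The documents do not support this. Profile size is not an outcome, no bias in the trait-score t-tests or in the T2/T3 ANOVA is shown, and the counts depend on distribution shape: with untransformed log-normal values (assumed log SD 1), the true matching count is about 13 of 50, not 25. Splitting rest for the clustering would also lower correct placement from 59% to 53% (R = .8, s = .5).

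**Conclusion.** The point holds in limited form. If flexibility is either rest-containing Delta, its correlation with tone is lower than it would be with an equally precise resting value carrying separate error, and the plan has no safeguard. For an overall Pearson test with no true association, rejection at reliability .8 and change SD .5 is about 44% with independent errors, falling to about 32%, 19% and 9% to 10% as a quarter, half or three quarters of the error is shared by rest and task. All of these rest on assumed inputs.

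It would be tempting to conclude that the trial's findings are at risk. That goes too far. The main group-by-time ANOVA does not use the tone–Delta correlation, bias in Analyses A, B or C is not shown, and the stated comparison stays near 5% if tested formally. The firm defects are the unnamed Delta, the unstated direction and the missing test. This is a cheap improvement to a secondary analysis, of minor severity.

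**What to change.** 1. Name the Delta that defines flexibility and say whether a larger fall or a larger rise counts as high.
2. If that Delta contains rest, run the correlational analysis with a resting value that does not share its error. T2 rest against the T1 Delta is preferable, since T2 rest also precedes training and is full length. Separate blocks of the 30-minute T1 rest are the alternative. Report the coupled correlation as secondary only. If recovery minus task is chosen, this step is not needed.
3. Test the claim of a stronger correlation by a formal comparison of the two correlations, such as Fisher z, and not by reading significance cell by cell.
4. Keep the K-means profiles for Analyses B and C on full T1 rest as planned, and do not read the profile counts as evidence of a tone–flexibility link.

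The cost is SAP wording and a re-run on data already collected. T2 rest loses patients without a T2 recording and adds between-session variation. Split rest is noisier and keeps some coupling if error persists across segments (about 12% rejection if half of it is shared, at R = .8 and s = .5). Power is low either way. In the same setting, a true r of .37 in either direction is detected in about 20% of trials with split rest. With full-length T2 rest, r = .2/√(1.25 × .79) = .20, and Φ(.204 × √47 − 1.96) gives about 29% before any between-session variation.

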[figure not shown]
¹ The bloc 1 will not be included in the final statistical analysis because is considered as a training bloc. This choice in accordance to the potential biases related to the increase of the sympathetic activity at the beginning of the task caused by a simple moving to action following the resting period.

second session, a short training session of the biofeedback [BFB] technique will be done and the software using for the biofeedback training will be supplied to each participant included in the experimental group to allowed to us to practice BFB by their self at home. The installation of the program and the explanations needed for using it, will be done during the second session (T2). The BFB software (Emwave Pro®) includes a photoplethysmography sensor that can be positioned on the earlobe. The participants will have to practice the biofeedback technique the next 24 days (3X5 min/day).

The period (24 days) between the second session and the third session (T2-T3) will be considered as the intervention period. At the end of the second session (T2), the participants will be separated into two inter-subject groups: an experimental group performing BFB technique (3X5 min per day) in the intervention period (T2-T3) and a control group not performing a specific exercise in the intervention period (T2-T3). The first 40 participants (20 IBS / 20 PNES) will be included into the experimental group (BFB training) whereas the last 10 participants (5 IBS / 5 PNES) will be included into the control group (no training). The participants won't be informed of the condition to which they belong. We will measure the parameters of interest before (T2) and at the end of the intervention period (T3). During the intervention period, all the participants will have to answer to online questionnaires (BVAQ-B, LES, DHS) aiming to examine the psychological profile (alexithymia, traumatic events).

The third session (T3), T2 + 24 days, will be similar of the two previous sessions. We will use the same questionnaires and will record the same electrophysiological parameters. Finally, a debriefing will be done at the end of the session for each participant. The session will be considered as the end of the study visit.

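### The tone–flexibility hypothesis is tested by comparing correlations between profiles cut on the same two variables, which gives about 8 to 16% power and leaves out the evidence that bears on it

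*Combined protocol and SAP*

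**What the plan says.** Under Analyse B, the SAP forms profiles in two separate runs: "two K means non-hierarchical clustering will be performed with K = 2". The variables are given as "One with HF or RMSSD and one with Δ HF or Δ RMSSD", the first for tone and the second for flexibility. Under Independent variables, only matching pairs are named, for example "A dysfunctional neurovegetative profile (low vagal tone + low vagal flexibility) group" and its high–high counterpart. No group is defined for people who are low on one and high on the other.

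The Correlational analysis then plans regressions or Pearson correlations "in order to test our hypothesis about the HF/RMSSD related to the 'low vagal tone' profile will be more correlated to" Δ in the low-flexibility profile than to Δ in the high-flexibility profile, and the reverse for high tone. The SAP names no test for comparing two correlations, no sidedness, no minimum cell size and no rule for an empty cell.

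Three Δs are defined for the task. The first is "Δ = reactivity HRV – resting HRV"; the others are recovery minus reactivity and recovery minus resting. The SAP does not say which one defines flexibility.

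**The concern.** The matching profiles suggest that the idea under test is that low tone goes with low flexibility, and high with high. An association of that kind shows in two places: the correlation over all participants, and the number of people in matching versus non-matching cells. The planned comparison uses neither. It asks whether tone and Δ correlate more strongly inside one cell than inside another.

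Cutting on both variables narrows their range and shrinks every correlation, so a difference between cells depends largely on where the cuts fall. The stronger the true association, the fewer people remain in the non-matching cell. The plan could therefore hold data that support its hypothesis well and still have little chance of showing it.

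**Working it through.** **The plan's own figure.** The only sample-size figure is 22, for the repeated-measures ANOVA (SAP, Sample). With f = √(.12/.88) = 0.369, 2 groups, 3 measurements, and an assumed correlation of 0.5 between measurements with epsilon = 1, λ = f²·N·3/(1 − 0.5) = 0.1364 × 22 × 3 / 0.5 = 18.0 on 2 and 40 df. Power is 0.964 (0.944 at N = 20), so 22 reproduces. It does not cover this hypothesis.

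**Inputs.** N = 40 + 10 = 50 (Study protocol, allocation at T2). The Sample section gives 25 + 22 = 47 as written, although its own bracket gives 20 + 5 = 25 for the second group. Cuts: two-cluster K-means on each variable. Assumed: bivariate normal tone and Δ, the true correlation ρ, and a Fisher z comparison at one-sided 5%, which needs at least 4 people per cell.

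**Formula.** Within a tone profile, z = [atanh(r₁) − atanh(r₂)] / √[1/(n₁ − 3) + 1/(n₂ − 3)], where 1 is the matching and 2 the non-matching cell.

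**Simulation, N = 50, K-means cuts**

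| ρ | Median cell sizes (matching / non-matching) | Mean r in those cells | Success per comparison | At least one comparison with a cell below 4 |
|---|---|---|---|---|
| .5 | 16 / 8 | .25 / .12 | about 8% | about 20% |
| .7 | 18 / 6 | .44 / .16 | about 10% | about 49% |
| .9 | 21 / 3 | .75 / .21 | 11–16% | about 92% |

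**Check by hand.**
- ρ = .5: atanh(.25) − atanh(.12) = 0.255 − 0.121 = 0.135; standard error √(1/13 + 1/5) = 0.526; ratio 0.26. The chance of exceeding 1.645 is 1 − Φ(1.39) = 8%.
- ρ = .7: 0.472 − 0.161 = 0.311; standard error √(1/15 + 1/3) = 0.632; ratio 0.49; 1 − Φ(1.15) = 12%. The simulated figure is lower because trials with a cell that is too small count as failures.
- ρ = .9: at the median sizes n₂ − 3 = 0, so z is undefined.

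**Sensitivity.**
- A two-sided test gives 4–5%, 6% and 9–10% in the hypothesised direction. N = 47 and N = 40 are the same or worse.
- With lognormal data, power is at most 6% (two-sided). At least one comparison has a cell below 4 in 91% of trials at ρ = 0 and in 82–99.7% for ρ from .3 to .95.

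**Would a plain whole-sample correlation do?** For bivariate normal tone and Δ it succeeds in 96% of trials at ρ = .5 and 100% at .7. That does not carry over to a Δ that subtracts rest. If resting value R and task value T are unrelated, corr(R, T − R) = −σ_R/√(σ_R² + σ_T²). With σ_T = 0.7σ_R this is −1/√1.49 = −0.82; with σ_T = σ_R it is −1/√2 = −0.71. At N = 50, a plain correlation or a 2×2 test of the clusters is then significant in about 94–100% of trials, with no link between rest and task.

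**The case against.** **The within-cell comparison is partly inferred.** The SAP names no comparison test and also allows regressions. This stands as a caveat on the exact percentages. It does not remove the problem, because any contrast of slopes or correlations between these profiles, on values paired by person, uses the same four cells.

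**The sponsor may mean the sentence literally**, as a difference between within-cell correlations. Power is still low: for true values of .5 against 0, two-sided Fisher z gives 22% with cells of 13 and 12, 18% with 17 and 8, and 11% with 20 and 5. Only extreme differences are detectable (.9 against 0 in cells of 13 and 12: 89%).

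**A reader might infer that the test becomes impossible to compute as the hypothesis becomes truer.** That is too strong. The limit of 4 belongs to a Fisher z test that the plan does not name; a Pearson r can be formed with 3 people. Under median cuts, a cell below 4 occurs in only about 0.1% of comparisons at ρ = .5 and 2.6% at .7. With skewed data small cells are common at every ρ, so the gradient belongs to roughly normal data.

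**A reader might also infer that a null result would be taken as evidence against the hypothesis.** The documents do not say how a null result would be read.

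**Conclusion.** The concern holds for this one hypothesis. Followed as written, the analysis has about 8 to 16% power per comparison over true correlations from .5 to .9, against a 5% chance of success with no association, and it does not use the cell counts. These figures rest on normal data, N = 50, one-sided Fisher z and an assumed ρ; the low power persists under the two-sided and skewed variants. Reading the hypothesis as an overall link between tone and flexibility is an interpretation, supported by the matching-only profiles.

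It would go beyond the documents to extend this to the trial's main result. The main criterion is vagal tone HF, analysed by ANOVA, and it does not depend on this bullet. Nor do the 96% and 100% above show what power the sponsor would gain: for the two Δs that contain rest, a plain correlation would be significant almost regardless of the truth.

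**What to change.** Replace the bullet with one whole-sample analysis of T1 tone and T1 flexibility, reported with a 95% CI, and drop the within-profile comparisons. Add a cross-tabulation of the tone and flexibility clusters with kappa, as description only.

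State which Δ defines flexibility and its sign, that is, whether a larger fall under the task counts as more flexibility. Then choose one of these in advance:
- **Recovery minus reactivity**, which does not contain rest. A plain correlation is then usable; N = 50 gives 80% power for r = tanh[(1.96 + 0.84)/√47] = 0.39.
- **Regression of task-period ln HF on resting ln HF**, reporting the slope with its CI. Name the reference value: a slope of 0 means that rest and task are unrelated, a slope of 1 that rest and Δ are unrelated.
- **Oldham's method**, Δ against the mean of rest and task, on the ln scale. It in effect compares the two variances. With unrelated rest and task its expected correlation is (σ_T² − σ_R²)/(σ_T² + σ_R²): 0 when the SDs are equal, but (0.49 − 1)/1.49 = −0.34 when the task SD is 0.7 of the resting SD. The SAP should say that this is the question being asked.

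The cost is SAP wording, with fewer tests and no new data. The downside is that the question is answered as an overall association rather than profile by profile.

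### The Sample section's 22 participants for power .95 does not fit a partial eta squared of .12 on the planned ANOVA's own scale, where power is about .51 at 22 and .90 or .72 at 50; the scale of .12 must be stated

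*Combined protocol and SAP*

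**What the plan says.** The Sample section describes an a priori G*Power calculation. It names the test family ("The power analysis, for an ANOVA (repeated measures, within-between factors"), gives the effect as a partial eta squared "of .12 with a power of .95 on the main judgment criterion" (that criterion being HF), "and reported a necessary sample of at least 22 participants", and cites three studies. It does not give the effect-size option chosen in the software, the correlation between sessions, the sphericity correction, the numbers of groups and measurements entered, or how .12 was obtained from the cited studies.

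Under Statistical analyses, Analysis A is "An ANOVA to repeated measurement with an intra factor (measurement time: T1 / T2 / T3) and an inter factor (group: experimental / control". The same section sets alpha at .05 and names the software that would report the effect size: "All statistical analyses will be performed using IBM SPSS Statistics", with R and JASP.

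The study protocol part puts the first 40 participants in the biofeedback group and the last 10 in the control group, 50 in all. The Sample section prints 25 IBS and 22 PNES patients, but its bracket for PNES adds to 25, so the planned total reads as 47 or 50. No power is stated for either total.

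**The concern.** In a repeated-measures ANOVA, partial eta squared for the time-by-group interaction is the effect sum of squares divided by the effect plus within-subject error sums of squares. The within-subject error is already reduced by the correlation between sessions. A power formula that takes this value and then divides by one minus the correlation uses the correlation twice, and the required sample comes out too small.

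This sentence is the plan's only power justification, and it concerns the main criterion. A reader who sees .12 and .95 will think the trial was sized for an interaction that the ANOVA output would print as .12. If the calculation in fact assumed a much larger effect, that reader would take a non-significant HF result as stronger evidence against an effect of .12 than it is.

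**Working it through.** **Inputs.** From the Sample section: partial eta squared .12, target power .95, stated N 22. From Statistical analyses: k = 2 groups, m = 3 sessions, alpha .05 (stated for the analyses and assumed for the power calculation). From the study protocol part: allocation 40:10. Assumed: epsilon = 1 unless noted.

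f² = .12/(1 − .12) = .12/.88 = .1364, so f = .369. The test is the interaction F with df1 = (k−1)(m−1) = 2 and df2 = (N−2)·2. Power comes from the noncentral F distribution with noncentrality λ.

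**1. Reproducing the plan's 22.** The default parametrisation is λ = f²·N·m/(1 − ρ). With ρ = .5:

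- N = 20: λ = .1364 × 20 × 3/.5 = 16.36, df 2 and 36, power .944.
- N = 22: λ = .1364 × 22 × 3/.5 = 18.0, df 2 and 40, power .964.

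So 22 is the smallest equal-group total that reaches .95. With k = 2 and m = 3, correlations of 0, .3, .4, .6 and .7 give 40, 30, 26, 18 and 14 instead.

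**2. What those inputs mean on the ANOVA scale.** With λ = 18 on 40 error df, the corresponding partial eta squared is (18/40)/(1 + 18/40) = 18/58 = .31. If the interaction lies wholly in the change from the mean of T1 and T2 to T3, that contrast has within-person variance (1 − .5) × 1.5 = .75 (HF SD = 1). With 11 per group, λ = δ² × 5.5/.75, so δ = √(18 × .75/5.5) = 1.57 SD of HF between groups.

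**3. Power if .12 is on the ANOVA scale.** Here λ = f²·(N − 2)·(m − 1), with no separate ρ. The Cohen-type variant replaces N − 2 by N. If .12 is defined for equal groups, a 40:10 split multiplies λ by 4 × .8 × .2 = .64.

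| Case | λ | Power | Cohen-type power |
|---|---|---|---|
| N = 22, equal groups | .1364 × 20 × 2 = 5.45 | .509 | .550 |
| N = 50, .12 holds in the 40:10 design | .1364 × 48 × 2 = 13.09 | .901 | .913 |
| N = 50 at 40:10, .12 defined for equal groups | 13.09 × .64 = 8.38 | .724 | .743 |
| N = 60, equal groups | .1364 × 58 × 2 = 15.82 | .9496 | .956 |
| N = 62, equal groups | .1364 × 60 × 2 = 16.36 | .956 | .962 |

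Two equal groups need 62 for .95 (60 on the Cohen-type variant). At 4:1, with .12 defined for equal groups, about 95 are needed. Simulation of the 3 × 2 ANOVA (20,000 runs per case, correlations .3, .5 and .8) gave .51–.52, .90–.91 and .72–.73 for the first three rows, with no dependence on the correlation.

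**4. Sensitivity.** With epsilon .75, the first three rows fall to .43, .83 and .63. If enrolment is 47, power is about .88 with equal groups, and about .71 with an assumed 37:10 split when .12 is defined for equal groups.

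**5. Power if .12 is relative to the between-person SD.** Then 22 is right. At 50 split 40:10, λ = .1364 × 50 × 3/.5 × .64 = 26.18 and power is .997.

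**The case against.** The strongest reply is that the diagnosis rests on settings the plan does not give. Other settings also return 22: two measurements with ρ = .6 under the default formula (power .957), or nine measurements on the Cohen-type ANOVA scale (power .951), nine being three sessions by three recording periods. So 22 by itself does not prove which option was used. This stands. Three sessions with ρ = .5 is the most natural match because Analysis A names exactly T1, T2 and T3 and two groups, but it remains an inference.

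Second, the plan does not say how .12 was derived. If it was expressed against the between-person SD, there is no shortfall. This also stands. A reader might infer that the calculation is a proven arithmetic error, or that the trial lacks the power it claims. The documents support neither without the condition that .12 is on the ANOVA scale. The symbol points that way but does not settle it.

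Third, nobody plans to enrol only 22, so .51 is not the power of the trial as planned. That is fair: at 50 the figure is .90 if .12 holds in the 40:10 design. A reader might take .72 as following from the same premise, but it needs the separate assumption that .12 describes equal groups.

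What the objection does not remove is that, for the planned two-group, three-session analysis, neither ANOVA-scale variant gives more than .55 at 22. That result needs no assumed correlation, and sphericity is the favourable assumption.

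**Conclusion.** The point holds conditionally. For the planned 3 × 2 analysis, a partial eta squared of .12 as the ANOVA reports it does not give power .95 with 22 participants; it gives about .51. The stated 22 is most naturally explained by a calculation whose inputs correspond to about .31 on that scale. At the planned 50, power for .12 is about .90 or about .72, depending on whether .12 describes the 40:10 design or equal groups.

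This rests on alpha .05, epsilon 1 and .12 being on the scale its symbol denotes. If .12 is instead relative to the between-person SD with ρ = .5, the sample size is right and the planned 50 have ample power for that much larger effect, but the label in the Sample section then misleads. Under either reading the sentence should be restated; the case for changing it does not depend on which reading is true.

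**What to change.** Keep enrolment and rewrite the power sentence on one scale, stating the effect-size option, the correlation (where used), epsilon, the number of groups and sessions, and how .12 was obtained. Either:

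- *Partial eta squared .12 as reported by the ANOVA needs 62 participants in two equal groups for power .95 (2 groups, 3 sessions, alpha .05, epsilon 1). The planned 50 (40:10) give about .90 if .12 applies to the 40:10 design and about .72 if it applies to equal groups. Non-sphericity lowers these figures.*

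Or, if .12 was meant relative to the between-person SD:

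- *f = .37, ρ = .5, epsilon = 1, 3 sessions, corresponding to an ANOVA partial eta squared of about .31. On this basis 22 participants are needed for power .95, and the planned 50 (40:10) give about .997.*

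Reconcile the PNES count (22 or 25) at the same time, so that the power refers to one total. The cost is one paragraph, with no change to enrolment or conduct. The downside is that the first version reports a less favourable power than the plan now does.
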